## **Endpoints**

### Primary endpoint.

[figure not shown]
Mean rate of change of FEV1 over 24 months on doxycycline compared with placebo.

### Secondary endpoints

Comparison between the two groups for:

- Rate of change of FVC over 24 months
- Change in DLCO at 12 and 24 months
- Change in shuttle walk distance at 12 and 24 months
- Change in quality of life at 12 and 24 months
- Time to composite safety endpoint
- Number of complications - pneumothorax, pleural effusions, angiomyolipoma bleeding
- Number of respiratory infections
- Adverse effects

# Flow chart

**Table2: Data capture summary**

Visit (months)	Screening	2 wk	1	2	3	6	9	12	15	18	21	24
History and exam	✓				✓	✓	✓	✓	✓	✓	✓	✓
Blood tests (1)	✓	✓			✓	✓	✓	✓	✓	✓	✓	✓
Urine zymography	✓		✓	✓	✓			✓				✓
Pregnancy test	✓				✓	✓	✓	✓	✓	✓	✓	✓
Serum MMPs	✓							✓				✓
Quality of life	✓							✓				✓
Urinalysis	✓				✓	✓	✓	✓	✓	✓	✓	✓
Chest X-ray	✓											
Spirometry	✓				✓	✓	✓	✓	✓	✓	✓	✓
Full lung function (2)	✓							✓				✓
Review of epilepsy (3)	✓	✓			✓	✓	✓	✓	✓	✓	✓	✓

A study phone call will take place at 2 weeks, 4, 5, 7, 8, 10, 11,13, 14, 16, 17, 19, 20, 22, and 23 months to ensure no problems have developed.

1. renal profile, liver profile, bone profile, glucose, thyroid function, amylase, full blood count and differential. 2. Spirometry, lung volumes, gas transfer and shuttle walk test with oxygen saturation. 3 only in patients with TSC.

### Study procedures

#### **Medical history and examination.**

At baseline and subsequent visits patients will undergo a full medical history concerning LAM, TSC and their complications, general medical history, drug treatment and sensitivities. At follow up visits patients will be specifically asked about compliance, any changes in medication and adverse events since the previous visit.

#### **Blood tests.**

At baseline, blood will be taken for FBC, U&E, LFT, glucose, calcium analysed in Chemical Pathology and Haematology Departments of the Queens Medical Centre, Nottingham using standard procedures.

At the same time serum will be taken for biomarker analysis, serum MMP-2, -9 and -7. These samples will be frozen and analysed by the study team at a later point using specific MMP ELISA (R&D systems) according to the manufacturer's instructions. Blood for biomarkers will be saved for later analysis.

**Lung function tests.** Spirometry, lung volumes, gas transfer and shuttle walk test will be performed by according to British Thoracic Society guidelines in the lung function unit Queens Medical Centre, Nottingham.

**Spirometry.** Spirometry alone will be performed according to BTS guidelines using a Vitalograph wedge bellows spirometer by a trained member of the study team.

**Serum and Urine zymography.** Zymography will be performed by a person independent of the study team using standard procedures. Briefly MMPs will be identified by gelatin zymography of serum and urine. Ten microlitres of sample (diluted

1:2 in 2x SDS sample buffer) will be run under non-denaturing conditions into precast Novex polyacrylamide zymogram gels (Invitrogen, Paisley, U.K.), supplemented with 0.1% gelatin with electrophoresis performed at a constant voltage of 125V for 90 min. Gels will be washed in re-naturing buffer and incubated overnight in developing buffer according to manufacturers guidelines, stained with 0.5% coomassie blue R-250 (in 50% water, 40% methanol; 10% acetic acid) and destained (in 50% water, 40% methanol; 10% acetic acid). Areas of gelatinolytic activity appearing as transparent bands will be analysed by densitometry and compared with a standard recombinant protein.

**LAM Cell isolation.** Heparinised blood is layered over histopaque (at 1:1 ratio) and centrifuged at 1500rpm for 30minutes at 22°C. The resulting buffy layer containing mononuclear cells is decanted into a 50ml tube and filled with HBSS. The cells are spun for 10mins at 1500rpm, the supernatant removed and the pellet resuspended in HBSS. After two further spins the resulting cells are cultured in fibronectin coated flasks. After 7-14 days resultant adherent cells are characterised by immunohistochemistry.

**Quality of Life assessment.** Will be assessed by the St Georges Respiratory Questionnaire and Chronic Respiratory Disease Questionnaire administered by the study team.

**Pregnancy testing.** Will be performed by urine  $\beta$ HCG analysis.

**Storage of samples.** All study samples will be stored in locked freezers in the Division of Therapeutics and Molecular Medicine, University of Nottingham. All samples will be stored in conjunction with current Human Tissue Act regulations.

#### Additional research procedures

**CT scanning.** In order to assess the effect of doxycycline on cystic change in the lungs and abdominal complications of LAM, a subset of patients will undergo CT scanning at the start and end of the study. Patients will consent specifically for this extra procedure.

**Research blood sample.** Patients who provide additional consent will undergo a blood test on the first visit and at the end of the study. This will be used for examination of gene and protein expression of relevance to LAM. In addition DNA will be removed and stored and genetic analysis performed on genes of relevance to LAM.

## 4. Data management

### Statistical advice

Statistical advice and analysis of the study results will be performed by the trial statistician, [name].

### Statistical analysis of endpoints

#### Primary endpoint

The primary endpoint will be the difference in rate of decline of FEV1 (ml/year) measured over 24 months.

All data will be analysed on an intention to treat basis in conjunction with the trial statistician [name]. The mean slope of regression lines for FEV1 and FVC, plus change in DLCO, shuttle walk distance and quality of life in the doxycycline and placebo groups will be compared by parametric or non-parametric analysis as appropriate following analysis of the data for normality. In addition we will perform a *per protocol* analysis of mean rate of change of FEV1/year. Time to composite safety endpoint will be analysed by Kaplan-Meier analysis, complications and adverse events by Chi Square test. Patients withdrawing from the study will continue to have measurements made where possible for intention to treat analysis. Missing values will be handled by multiple imputation.

#### Secondary endpoints

- The mean of regression lines for FVC measurements for each group (nine measurements per subject) will be compared by unpaired t-test with 0.05 taken as statistical significance. Patients will be analysed on an intention to treat basis with those withdrawing for any reason (including the combined safety criteria) will be analysed up to withdrawal.
- Change DLCO, shuttle walk distance and QoL in the doxycycline and placebo groups will be compared by parametric or non-parametric analysis. Data will be analysed for normality using the Kolmogorov-Smirnov method.

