#### Sample size

Power calculations have been based on several retrospective cohorts. In our UK national study the rate of decline in FEV1 for all patients was 118 ml/yr (SD=142, n=43) and 106 ml/yr (SD=143, n=57) in a similar French cohort. In a larger study of less severely affected patients from the NIH the overall yearly rate of decline in FEV1 was 75 ml/yr (SD=149, n=275). All of these studies have used data from retrospective series performed at different sites at different times. Using prospective standardised measurements performed by the same operators we expect the variation in change in FEV1 to be smaller than observed in these cohorts. Using 20 patients per group there will 80% power to detect a difference of 70 ml/year difference in FEV1 based on the assumption that the SD of the fall in FEV1 in the trial is 75 ml/year.

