#### Management of adverse events associated with doxycycline

**Gastrointestinal.** To reduce the risk of oesophagitis enteric-coated capsules will be used and patients will be advised to take doxycycline at meal times with a full glass of water. If these measures are unsuccessful, we will withdraw the drug and ask the patient to be evaluated by a gastroenterologist.

**Cutaneous.** Patients will be advised about the risk of photosensitivity, and to use good sun protection. For patients in whom a significant episode of tetracycline-induced

photosensitivity develops, treatment with doxycycline will be interrupted for a week to allow resolution of the skin reaction. Methods to protect the skin from exposure to light will be discussed with the patient, and doxycycline treatment will be resumed at the same dose. If this is unsuccessful in preventing further photosensitivity reactions, patients will be withdrawn from the study.

**Dental.** For patients in whom tooth discoloration develops, vigorous oral hygiene will be advised, along with regular follow-up with a dental technician for formal cleansing. Patients will be advised not to use chlorhexidine-containing mouthwashes, which can cause tooth discoloration. If this is unsuccessful in resolving tooth discoloration to the patient's satisfaction, the patient will be removed from the study.

**Infectious.** Doxycycline may cause moderate changes in oropharyngeal and colonic microflora. Non-antimicrobial doses of doxycycline do not appear to have an effect on the composition or resistance of faecal or vaginal microflora (167). It is possible that patients may become colonized with doxycycline resistant organisms. For patients in whom any form of yeast infection developed during the course of the study, doxycycline treatment may be interrupted to permit resolution of the infection, along with vigorous hygiene and anti-fungal treatment, followed by resumption of the study medication.

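### The protocol gives two contradictory rules for FVC data after withdrawal, and the rule that cuts the data is wrongly labelled intention to treat

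*Protocol*

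**What the plan says.** Three places in the protocol bear on this.

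- **Statistical analysis of endpoints, Primary endpoint.** All data are to be analysed by intention to treat, and the slopes of both FEV1 and FVC are named in that paragraph. It adds: "Patients withdrawing from the study will continue to have measurements made where possible for intention to treat analysis". It then says: "Missing values will be handled by multiple imputation".
- **Statistical analysis of endpoints, Secondary endpoints, FVC bullet.** FVC regression lines from nine measurements per subject are to be "compared by unpaired t-test with 0.05 taken as statistical significance". The bullet claims an intention-to-treat basis but continues: "those withdrawing for any reason (including the combined safety criteria) will be analysed up to withdrawal".
- **Combined safety endpoint.** A fall in FEV1 of 300 ml or in resting SaO2 of 3%, on two occasions, leads to unblinding and an offer of doxycycline on placebo, or to withdrawal at the doctor's discretion on doxycycline. Pneumothorax, increased chylous effusion or a bleeding angiomyolipoma also leads to withdrawal. The Summary says patients meeting this endpoint are analysed by intention to treat.

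No section says which rule prevails for FVC.

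**The concern.** This is not a detail left for a statistical analysis plan. The protocol settles the point twice, in opposite ways, so an analysis plan that follows one section breaches the other. The two rules can give different FVC results from the same data, and a choice made after the data are seen would be open to challenge.

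The label is also wrong. Discarding readings that the protocol elsewhere tells staff to collect estimates change while patients remain in the study. That is not an intention-to-treat analysis.

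The cutting rule is the weaker of the two on its merits. It gives a short, noisy slope the same influence as a full one. It also cuts the series at a point that can depend on a low FEV1, which is likely to be related to FVC, and that point is reached more often on placebo if the drug works.

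**Working it through.** **1. The plan's own figure.** The Sample size section states: "Using 20 patients per group there will 80% power to detect a difference of 70 ml/year", assuming that the SD of the fall in FEV1 "in the trial is 75 ml/year". I take alpha as two-sided 0.05; the protocol gives 0.05 without sidedness.

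n per group = 2 × (1.960 + 0.842)² × 75² / 70² = 18.02, rounded up to 19. The exact t-test gives 79.9% power at 19 and 82.0% at 20, so 20 per group reproduces. This calculation is for FEV1. The protocol gives no target difference, SD or power for FVC.

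**2. Precision of a slope that is cut short.** For one patient's least-squares slope, error variance = residual variance / Sxx, where Sxx is the sum of squared deviations of the visit times in years. Visits are quarterly.

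| Last reading | Readings | Sxx | Error variance relative to a completer |
|---|---|---|---|
| Month 24 | 9 | 0.0625 × 60 = 3.75 | 1 |
| Month 12 | 5 | 0.0625 × 10 = 0.625 | 3.75 / 0.625 = 6 |
| Month 6 | 3 | 0.0625 × 2 = 0.125 | 3.75 / 0.125 = 30 |

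These ratios need no assumption beyond the visit schedule. Equal weighting is inferred from the unpaired t-test on regression lines; no weighting is stated.

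**3. What this does to the SD.** Take a completer slope SD of 75 ml/yr and assume a residual SD of 75 ml.

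- Completer error variance: 75² / 3.75 = 1,500, which leaves 5,625 − 1,500 = 4,125 between patients.
- Variance of a slope ending at month 6: 4,125 + 75² / 0.125 = 49,125.
- If 2 of 20 patients in an arm stop at month 6 (an assumed case): mean variance = (18 × 5,625 + 2 × 49,125) / 20 = 9,975, an SD of about 100 instead of 75. The same sum gives about 87 with residual SD 50 and about 116 with residual SD 100.

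**4. Bias in FVC.** I used simulated trials of 20 v 20 with nine visits and linear decline. Withdrawal followed a 300 ml FEV1 fall at two visits, plus 10% a year at random, and FVC slopes were cut there and compared by t-test. FVC was given the FEV1 planning values as a stand-in: decline 118 ml/yr on placebo (the UK cohort figure in Sample size), true difference 70, slope SD 75. Residual SD, random withdrawal rate and correlation are assumptions.

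| Correlation of FVC with FEV1 | Bias (ml/yr) at residual SD 50 / 75 / 100 | Slope SD |
|---|---|---|
| 0.8 | +1.2 / +4.0 / +8.0 | 93 / 113 / 144 |
| 0 | −0.1 / 0.0 / +0.2 | 91 / 110 / 134 |

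With no drug effect, and the analysed measure itself driving withdrawal, bias was 0.0 and −0.4 ml/yr at residual SD 50 and 100, and the rejection rate was about 5%. With complete readings, bias was about zero and power 81 to 82%.

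**5. If the same cut were applied to FEV1.** Power at residual SD 50 / 75 / 100, against 81 to 82% with complete readings:

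- FEV1 rule only: 81 / 77 / 66%.
- Plus 5% a year random withdrawal: 75 / 67 / 55%.
- Plus 10% a year random withdrawal: 67 / 57 / 45%.

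**The case against.** The strongest defence is about scope. The cutting sentence stands inside the FVC bullet under Secondary endpoints. A reader might infer from its general wording that it is the trial's rule for every slope, and so that the primary comparison loses power. The document does not support that, because the Primary endpoint section has its own rule and that rule keeps the data. The power figures in step 5 are therefore hypothetical for this protocol.

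Other parts of the defence also stand:

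- FVC is not itself a withdrawal trigger. The bias needs both a working drug and a link between FVC and FEV1. A reader might infer a raised false-positive risk; the no-effect runs show none.
- Much of the precision loss comes from assumed withdrawal unrelated to FEV1. The FEV1 rule rarely leaves only three readings: about 0.2% of placebo patients at an assumed residual SD of 80 ml. The protocol states no expected dropout.
- The simulations cut everyone who meets the FEV1 rule. The Summary and the Combined safety endpoint section leave some of these patients the possibility of staying in the study.
- The adverse-event section has patients leave the study, for example if advice and a pause do not succeed "in preventing further photosensitivity reactions, patients will be withdrawn from the study". Since the Primary endpoint section already foresees measuring patients who withdraw, this is unclear wording and adds no further contradiction.

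None of this removes the conflict for FVC. The Primary endpoint section names FVC, and the FVC bullet cuts it.

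**Conclusion.** The contradiction is certain for the FVC slope, and the intention-to-treat label in the FVC bullet is wrong. The error-variance ratios of 6 at month 12 and 30 at month 6 follow from the visit schedule. Some loss of precision therefore follows whenever patients leave early and slopes count equally; its size depends on a residual SD and a withdrawal rate that the protocol does not give.

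The overstatement of an FVC benefit is conditional: about 1 to 8 ml/yr on a true 70 under the stand-in values and assumptions of step 4, and about zero without a drug effect or without correlation.

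The primary FEV1 analysis is not affected as written. A fall in FEV1 power from 82% to between about 45% and 80% would arise only if the FVC rule were carried over to it. This is a defect in a secondary analysis that should be corrected before any data are analysed.

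**What to change.** Delete from the FVC bullet the clause "those withdrawing for any reason (including the combined safety criteria) will be analysed up to withdrawal", with its joining word. State instead that FVC follows the Primary endpoint rule: all readings are used for both slopes, including those after study drug has stopped or after a move from placebo to doxycycline, and missing values are handled as stated there.

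Optionally, analyse all readings in a mixed model with a random intercept and slope per patient, so that short follow-up is weighted by the information it carries. On cut data with completer slope SD 75, such a model with variance components taken as known returned 69 to 70 ml/yr for a true 70, with power 77 to 84%. That check was not run on the all-readings analysis, so it supports the weighting only. The contradiction is resolved without this step.

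The Summary, the Combined safety endpoint section and the section on managing adverse events should be reconciled with the Primary endpoint section as to whether follow-up continues after a patient stops study drug or is withdrawn. No change to any clinical rule is proposed.

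The cost is one sentence and visits the protocol already intends where possible. There is one small statistical price. Readings after crossover dilute the contrast: if crossover patients gain the full effect, a true 70 is estimated at about 67 with residual SD 80 ml, and 63 to 65 with 120 ml (both SDs assumed). That is a legitimate treatment-policy effect. An analysis that sets values after crossover to missing can be reported as supplementary.

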## Additional protocol information

### **Randomisation.**

Randomisation will be handled by the Nottingham Clinical Trials Unit using a computer generated random sequence in a 1:1 ratio of drug to placebo. Randomisations will be performed by the study team via secure web based system hosted for the Nottingham Clinical Trials unit at the University of Nottingham.

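### DLCO, shuttle walk and QoL are compared as change with no baseline covariate named, and a normality check chooses the test, including for the primary FEV1 slopes; the FVC test is stated in two conflicting ways

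*Protocol*

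**What the plan says.** Section 3 of the protocol (Endpoints, Secondary endpoints) defines DLCO, shuttle walk distance and quality of life as changes at two time points, for example "Change in DLCO at 12 and 24 months". Under Initial Assessment and in Table 2, all three are measured on every patient at screening and again at 12 and 24 months.

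The analysis is stated in section 4, in two subsections:

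- **Primary endpoint.** FEV1 slopes, FVC slopes and the changes in DLCO, shuttle walk and QoL "will be compared by parametric or non-parametric analysis as appropriate following analysis of the data for normality". No particular normality test is named here.
- **Secondary endpoints.** "Change DLCO, shuttle walk distance and QoL in the doxycycline and placebo groups will be compared by parametric or non-parametric analysis". The check is then named: "Data will be analysed for normality using the Kolmogorov-Smirnov method". For FVC slopes, however, this subsection fixes the method outright: they are "compared by unpaired t-test with 0.05 taken as statistical significance".

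Neither subsection names a baseline covariate. Randomisation uses a "computer generated random sequence in a 1:1 ratio of drug to placebo", with no stratification factor named. The sample size rests on a difference in mean FEV1 decline: "Using 20 patients per group there will 80% power to detect a difference of 70 ml/year difference", assuming that the SD of the fall "in the trial is 75 ml/year".

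**The concern.** There are three separable problems.

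1. **Change without baseline.** A between-group comparison of raw change uses the baseline less efficiently than a model that conditions on it. It also leaves part of any chance baseline difference in the estimate. The trial has 40 patients and is meant to supply an effect size for planning a larger one, so precision matters.
2. **The data choose the test.** The choice between a parametric and a rank test is made after looking at the trial data, for the primary endpoint as well. The two tests address different quantities, so neither the test nor the reported effect measure is fixed in advance.
3. **FVC is specified twice.** One subsection makes the FVC test depend on the normality check; the next does not.

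Problem 1 costs precision. Problems 2 and 3 leave open which result counts as the planned one.

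**Working it through.** **The plan's own figure.** Inputs from Sample size: difference 70 ml/year, SD 75 ml/year, power 80%. Two-sided 5% is assumed: 0.05 is stated only for FVC, and sidedness is not stated.

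n per group = 2 × (1.96 + 0.842)² × (75/70)² = 2 × 7.85 × 1.148 = 18.02, so 19. The t-based calculation gives 19.03, so 20. Power at 20 per group is 83.9% (normal) or 82.0% (t). The stated 20 per group is reproduced as a comparison of two means.

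**Change score against ANCOVA.** Let s be the common SD at baseline and follow-up, and r their correlation. The protocol does not give r, so a range is assumed.

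- Change-score variance per patient: 2s²(1−r)
- ANCOVA residual variance per patient: s²(1−r²)
- Ratio: (1−r²) / [2(1−r)] = (1+r)/2
- Approximate small-sample cost of one covariate at N=40: 1 + 1/(40−4) = 37/36

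Extra patients are those a change-score analysis would need to match ANCOVA on 40, that is 40/ratio − 40. The power column assumes that the change-score analysis has 80% power and leaves out the 37/36 factor.

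| r | Ratio | Ratio × 37/36 | Extra patients (after 37/36) | ANCOVA power |
|---|---|---|---|---|
| 0.5 | 0.75 | 0.771 | 13 (12) | 90% |
| 0.7 | 0.85 | 0.874 | 7 (6) | 86% |
| 0.8 | 0.90 | 0.925 | 4 (3) | 84% |
| 0.9 | 0.95 | 0.976 | 2 (1) | 82% |

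Break-even: (1+r)/2 × 37/36 = 1 gives r = 72/37 − 1 = 0.946.

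**Chance imbalance.** With 20 per arm, the baseline difference has standard error √(2/20) = 0.32 SD. Its expected absolute size is 0.316 × √(2/π) = 0.25 SD. A change score keeps (1−r) of it: about 0.13 SD at r=0.5, 0.08 at 0.7 and 0.025 at 0.9.

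Table E1 in the supplement can serve as an illustration only. Baseline TLCO is 3.81 against 5.00, a difference of 1.19. The pooled SD is √[(11×1.98² + 10×1.87²)/21] = 1.93, so the gap is 0.62 SD. The retained share is 0.3 × 1.19 = 0.36 units at r=0.7 and 0.1 × 1.19 = 0.12 at r=0.9, in favour of doxycycline, whose baseline is lower.

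**The normality check.** Simulation with 4,000 runs and 20 per arm. Detection is per sample of 20. In the two-stage procedure, the rank test replaces the t-test if the Lilliefors version flags either arm.

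| True distribution | Plain Kolmogorov-Smirnov flags | Lilliefors version flags | Type I error, two-stage |
|---|---|---|---|
| Normal | 0.0% | 4.6% | 4.2% |
| t, 3 df | 2.7% | 24.8% | 5.5% |
| Exponential | 3.8% | 57.9% | 4.8% |
| Lognormal | 20.4% | 79.1% | 5.4% |

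The plain version has little power at this size. The protocol does not say which version applies, and with exponential data that detail moves the chance of a flag from about 4% to 58%.

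**FVC, side by side.** Primary endpoint subsection: test chosen after the normality check. Secondary endpoints subsection: unpaired t-test. If the check flags non-normality, the two give different instructions.

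**The case against.** The strongest reply is that the lack of adjustment is read from silence. A parametric analysis of change could include the baseline as a covariate, and covariates for secondary endpoints are commonly left to an SAP, which is not at hand. That stands in part: the protocol does not rule adjustment out. But it does state change as the outcome and a data-driven rule for choosing the test, and those can be judged as written.

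Several stronger readings are tempting and are not supported:

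- **That the comparison of change is biased.** Over repeated randomisation it is unbiased. The retained share of imbalance is a bias only conditional on the imbalance that occurs.
- **That large imbalance must be expected.** The typical size is 0.25 SD; a gap of 0.62 SD or more has about a 5% chance.
- **That Table E1 shows the plan to be at fault.** It is a results table on 12 and 11 patients. It illustrates arithmetic and says nothing about the plan. Its FEV1 difference is beside the point, since FEV1 is analysed by slope.
- **That the normality check causes the precision loss or inflates type I error.** The loss comes from the unadjusted change score. Simulated error stayed at 4.2 to 5.5% (Lilliefors version; the two-stage procedure with the plain version was not simulated).
- **That Kolmogorov-Smirnov is prescribed for the primary endpoint.** It is named only in the secondary endpoints subsection; the primary subsection refers to a normality analysis without naming a test.

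It is also fair to say that the gain is small for a highly repeatable measure, as DLCO may be, and that these are secondary endpoints of a self-described pilot.

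**Conclusion.** The point holds as an avoidable weakness in specification, plus one internal contradiction. It should be corrected, but it does not invalidate the trial.

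- For DLCO, shuttle walk and QoL, ANCOVA would cut variance by 25% at r=0.5, 15% at 0.7 and 5% at 0.9, before a small-sample cost of about 3%. The benefit is gone above about r=0.95. This rests on equal SDs and an assumed r.
- For all continuous endpoints, the primary one included, the harm of the normality check is that the test and the effect measure are not fixed. For FEV1, a switch to a rank test would depart from the comparison of means on which the 20 per group was calculated.
- The FVC contradiction needs no assumption: the two subsections of section 4 cannot both be followed if the data fail the check.

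The primary sample size is not affected by the adjustment question.

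**What to change.** In section 4 of the protocol:

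1. Analyse DLCO, shuttle walk distance and each QoL score at 12 and at 24 months by ANCOVA with the baseline value and treatment in the model. Report the adjusted difference with its 95% CI.
2. Delete the normality-based choice of test from both the primary and the secondary endpoints subsections, and make the same change in the Summary.
3. Name one parametric comparison of slopes for FEV1 and FVC, worded identically wherever it appears.
4. Keep a rank or permutation test as a pre-specified sensitivity analysis that does not replace the main result.

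The change is one of wording and needs no new data or visits. The price is one degree of freedom per ANCOVA model, which at 40 patients slightly outweighs the gain only if r exceeds about 0.95.
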